#### **5.6 Patient supply and return of the product**

The investigated products moxonidine and bisoprolol are intended only for patients participating in the study and should be used according to the protocol.

The patient will be provided with the required amount of the product at the enrollment visit (V1), visit V2, and visit V3 for subsequent treatment period till next visit.

The product will be provided to the patient in the course of the study only. The treatment will be discontinued at final visit V4.

The patients will be asked to bring all used and unused investigated products blisters to the study site at visits V2, V3, V4.

All defects and damages of the investigated product or its packaging must be reported to the study CRA. Additionally, the investigator must report any patient complaints to the study CRA (change in the product taste, appearance, etc.).

### **5.7 Product accountability**

The investigator and/or pharmacist and/or authorized site staff is responsible for the product accountability. The product accountability will be monitored by the CRA on a regular basis.

Sponsor will provide the investigated product accountability forms to document all the product shipments, distribution and return. The investigator and/or pharmacist and/or authorized site staff should fill out these forms in a timely manner. CRA must fill out the product return and disposal form after the end of the study.

## **6 EFFICACY EVALUATION**

Efficiency analysis will be carried out in the population of patients who completed the study according to the protocol.

### **6.1 Primary endpoint efficacy criteria:**

Changes in mean values of the bone resorption marker (collagen type 1 C-telopeptide) at the end of the study (V4) from the baseline (V1) in comparison between the groups.

### **6.2 Secondary endpoints efficacy criteria:**

1. Changes in mean values of the bone synthesis marker (osteocalcin) at the end of the study (V4) from the baseline (V1) and to compare the values between the groups.
2. Changes in mean values of the receptor activator of nuclear factor kappa-B ligand (RANKL) at visit 4 versus baseline level (visit 1) and to compare the values between the groups

3. Changes in mean values of BMD at visit 4 versus baseline level (visit 1) using control dual-energy X-ray absorptiometry and to compare the results between the groups
4. Changes in mean values of telomerase activity at visit 4 versus baseline level (visit 1) and to compare the values between the groups
5. Changes in mean values of pulse wave velocity (PWV) at visit 4 versus baseline level (visit 1) and to compare the values between the groups
6. Changes in mean values of intima-media thickness (IMT) at visit 4 versus baseline level (visit 1) and to compare the values between the groups
7. Proportion of the treatment responders (defined as the proportion (%) of patients who achieved target blood pressure <140/90 mmHg) after 8 and 48 weeks of the investigated treatment (V2, V3 and V4) and to compare the values between the groups.

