## **1. INTRODUCTION**

### **1.1 Rationale**

It is known that cardiovascular disease (CVD) associated with atherosclerosis is the major cause of morbidity, disability and mortality in developed countries and, according to WHO estimates, in the next decade, CVD may become the leading cause of death in developing countries as well [1]. At the same time, the CVD epidemic is unfolding in the setting of significant advances in the diagnosis and treatment of these conditions. One reason for such a dramatic increase in heart attack, stroke, and heart failure incidence is thought to be the steadily aging population. It is due to the fact that age-related changes of blood vessels are an important risk factor for CVD. Growing evidence has been accumulated that aging-related changes in the vascular wall produce metabolically and enzymatically active environment that promotes initiation and progression of vascular disease. The more pronounced the age-related vascular wall changes are, the easier and faster atherosclerosis, hypertension and other CV disorders develop, which, in turn, accelerates the age-related changes.

The main signs of vascular aging include arterial wall thickening, subclinical atherosclerosis, vascular calcification and increased arterial stiffness, of which the increased vascular stiffness is a key sign of vascular aging [2, 3]. It is known that aside from hypertension, the chronic indolent inflammation associated insulin resistance plays a fundamental role in the increase of vascular wall stiffness [4]. In recent years, more data have been accumulated on the role of cellular senescence in the development of vascular aging. One of the major theories of cellular senescence is based on the telomere shortening. A telomere is a region of repetitive nucleotide sequences (TTAGGG) at the end of a linear chromosomal DNA. The main mechanism for maintaining telomere length is the restoration of telomere repetitive DNA sequences by the enzyme telomerase. The assessment of telomerase enzyme activity in combination with other parameters enables to evaluate the rate of aging [5, 6]. Accelerated

telomere shortening and reduced telomerase activity may be due to oxidative stress, chronic inflammation and their associated processes, e.g., insulin resistance [7, 8].

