It is believed that vascular and cellular markers of aging may be a useful additional criterion for evaluation of long-term effectiveness of therapy for chronic non-infectious diseases, e.g., arterial hypertension.

The postmenopause is a period in a woman's life that is characterized by accelerated aging processes, higher risk of hypertension and progressive insulin resistance.

There is no doubt that the search for effective targeted therapy of the main chronic non-infectious diseases aimed at not only treatment of the disease but also at slowing of the aging itself is a very promising research area.

Earlier clinical trials revealed a positive effect of moxonidine on insulin resistance suggesting that the drug may be a promising antihypertensive agent with a potential effect on cellular and vascular aging [9].

Other antihypertensive drugs have a short-term effect on the functional state of the arterial wall (owing to smooth muscle relaxation) and a long-term effect on its structure (primarily due to quantitative and qualitative changes in elastin and collagen). A meta-analysis based on the results of 15 randomized clinical studies has demonstrated that the arterial stiffness may be reduced in patients administered with antihypertensive medications regardless of the intensity of the antihypertensive effect [10].

Reduction of arterial stiffness in hypertensive patients was noted for ACE inhibitors, beta blockers (BB), angiotensin II receptor blockers, and calcium antagonists [11].

Along with hypertension, **osteoporosis** is one of the most pressing problems of women's health. Among all known forms of osteoporosis, the postmenopausal osteoporosis accounts for 85% of all osteoporosis cases. As we age, the bone metabolism is shifted towards bone resorption that leads to osteopenia, and to osteoporosis in subjects predisposed to rapid loss of the bone mass [12]. Bone strength depends on the amount of bone mass and quality of the bone tissue. Bone mineral density (BMD) is the measure of bone mass, while the bone tissue quality is characterized by bone turnover that is evaluated with biochemical markers of bone formation (e.g., osteocalcin, OC) and bone resorption (e.g., collagen type 1 C-telopeptide, CTx).

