### **2.2 Secondary (experimental) objectives:**

To investigate the effect of moxonidine versus bisoprolol on bone metabolism and bone tissue density in postmenopausal female patients with essential hypertension and osteopenia.

To investigate the effect of moxonidine versus bisoprolol on the processes of cellular and vascular aging in postmenopausal female patients with essential hypertension and osteopenia.

To investigate efficacy of antihypertensive therapy with moxonidine versus bisoprolol in hypertensive postmenopausal women.

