### 3.5 Number of patients:

114 patients will be enrolled to the study to ensure the final sample size. The patients will be randomized to one of two treatment groups (moxonidine group or bisoprolol group) using simple

randomization envelopes. It is anticipated that a screening of 300 subjects will be needed in order to enroll the minimum of 100 patients to the study.

According to the study protocol, patients randomization to the control and investigated groups will be carried out randomly and, therefore, it is assumed that the control and the investigated groups will be matched by the basic measured parameters; the number of subjects in the main and control groups is planned to be equal.

The study endpoints are measured prior to the studied product initiation (V1) and after completion of 48-week treatment with the investigated product (V4).

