### **3.6.6 Final visit (V4)**

The investigator will document the disease history since the last visit, including all adverse events, changes in concomitant treatment, changes in concomitant medications doses, if any.

The investigator will analyze the effectiveness of the therapy according to the patient's BP self-monitoring diary data.

The investigator measures BP and HR according to the ESH/ESC recommendations that are listed in Appendix 1. Blood pressure and heart rate are measured in a sitting position after 5 minutes of rest. Two measurements are done; the average value of the measurements is documented. BP is measured on the same arm during the entire study. Full physical examination is not required.

Patient's biochemical blood analysis (total calcium, inorganic phosphorus) is performed. Blood is sampled to investigate bone metabolism: osteocalcin, Ctx, OPG, RANKL.

Blood is sampled to determine telomerase activity.

Dual energy X-ray absorptiometry to determine BMD and detect osteopenia is performed.

Applanation tonometry method is used to measure changes in patient's PWV; duplex ultrasonography of extracranial brachiocephalic arteries is employed to evaluate IMT and subclinical atherosclerosis.

The investigator evaluates the response to the treatment (target BP reaching) and documents it in the source documents, as well as estimates patient compliance based on amount of the returned investigated product.

After successful completion of visit V4 procedures, the patient completes her participation in the study. The investigated product is discontinued; further treatment is carried out according to the attending physician advice.

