**Secondary efficiency indicators:**

- Changes in mean values of telomerase at the end of the study (V4) from the baseline (V1).
- Changes in mean values of Hs-CRP, lipids, PWV and IMT at the end of the study (V4) from the baseline (V1).
- Changes in mean values of the bone synthesis and resorption markers (osteocalcin, collagen type 1 C-telopeptide) at the end of the study (V4) from the baseline (V1).
- Changes in mean values of the bone synthesis marker (osteocalcin) at the end of the study (V4) from the baseline (V1).
- Changes in mean values of the receptor activator of nuclear factor kappa-B ligand (RANKL) at the end of the study (V4) from the baseline (V1).
- Changes in mean values of BMD at the end of the study (V4) from the baseline (V1).

- Proportion of the treatment responders (defined as the proportion (%) of patients who achieved target blood pressure <140/90 mmHg) after 8, 24 and 48 weeks of the investigated treatment (V2, V3 and V4).

The treatment efficacy will be evaluated on visits V2, V3 and V4 based on SBP and DBP measurements. Clinical response to the treatment is defined as follows:

- Responders: hypertension control, if BP <140/90 mmHg at the visit.
- Non-responders: uncontrolled hypertension, if BP  $\geq$ 140/90 mmHg at the visit.

The efficacy results will be presented using descriptive statistics. Historical control (publications data) will be used to interpret the results.

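### The pulse wave velocity comparison estimates the total effect of the two treatment strategies; as planned, it cannot be read as a difference in vascular ageing

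*Combined protocol and SAP*

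**What the plan says.** Section 2.2 of the protocol sets the objective: "To investigate the effect of moxonidine versus bisoprolol on the processes of cellular and vascular aging". Section 1.1 lists several signs of vascular ageing, "of which the increased vascular stiffness is a key sign of vascular aging". Two endpoints in sections 3.10 and 6.2 serve the vascular part, PWV and IMT.

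For PWV, section 6.2 specifies: "Changes in mean values of pulse wave velocity (PWV) at visit 4 versus baseline level (visit 1) and to compare the values between the groups". Section 10.3 lists it without any between-group wording, as "Changes in mean values of Hs-CRP, lipids, PWV and IMT at the end of the study (V4) from the baseline (V1"). The same section says that efficacy will be presented descriptively and interpreted against published historical controls. No model or covariate is named.

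On timing, section 3.5 says: "The study endpoints are measured prior to the studied product initiation (V1) and after completion of 48-week treatment with the investigated product (V4"). On method, section 3.6.6 says only: "Applanation tonometry method is used to measure changes in patient's PWV". It sets no condition on BP or heart rate at the time of measurement.

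Section 1.1 also describes how antihypertensives act on the vessel wall: "Other antihypertensive drugs have a short-term effect on the functional state of the arterial wall (owing to smooth muscle relaxation) and a long-term effect on" (the sentence goes on to name the wall's structure as what changes in the long term). It then adds: "Reduction of arterial stiffness in hypertensive patients was noted for ACE inhibitors, beta blockers (BB), angiotensin II receptor blockers, and calcium antagonists".

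**The concern.** The conclusion sought is about vascular ageing, but the quantity compared is the raw change in PWV between two different haemodynamic states. The protocol itself separates a short-term functional action of antihypertensives from a long-term structural one. It also credits the add-on classes (ACE inhibitors and angiotensin receptor blockers) and the comparator's class (beta blockers) with lowering stiffness.

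If one arm reaches a lower pressure, a different heart rate or a different rate of add-on use, a PWV difference can appear with no difference in structural ageing, or a real one can be hidden. A publication could then credit slowed vascular ageing to what is partly pressure lowering or add-on therapy. The plan uses none of the data that would show this, although they are already being collected.

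**Working it through.** **State at each measurement**

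| | V1 | V4 |
|---|---|---|
| Treatment | Before the first dose; prior antihypertensives washed out or not being taken (4.4, 5.1) | Study drugs taken until week 48 and stopped at this visit (3.8.1 to 3.8.3, 5.1) |
| BP | Entry criteria must be met at enrolment, so above target (4.2, 4.4) | Target below 140/90 mmHg |
| Add-on | None | Perindopril, or losartan if not tolerated, in patients who missed target (3.1) |
| BP and heart rate recorded | Yes (7.2) | Yes (7.2) |

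PWV is measured at these two visits only (3.4).

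**What cancels and what does not**

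- Between arms, pressure lowering common to both cancels. Only an arm difference in BP, heart rate or add-on use remains.
- Within an arm, or against historical controls, nothing cancels.

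**Scale.** The plan states no PWV figure to reproduce: no slope, SD, target difference or power. The inputs marked (A) are assumptions.

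*Between arms.* Slope (A) 0.3 to 0.8 m/s per 10 mmHg mean arterial pressure; arm difference at V4 (A) 5 mmHg. PWV difference = slope × 5/10:

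- 0.3 × 0.5 = 0.15 m/s
- 0.5 × 0.5 = 0.25 m/s
- 0.8 × 0.5 = 0.40 m/s

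With equal pressures the result is 0.

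*Effect on a significance test.* SE = SD × √(2/57), with 57 per arm from section 3.2 and two-sided 0.05 from section 10.1. At SD 1.0 m/s, SE = 0.187. Probability of rejection, given that the 5 mmHg difference exists and there is no structural difference:

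| SD of change (A) | 0.15 m/s | 0.25 m/s | 0.40 m/s |
|---|---|---|---|
| 1.0 m/s | 12.6% | 26.6% | 57.0% |
| 1.5 m/s | 8.3% | 14.4% | 29.6% |

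*Add-on.* With a 20-point arm difference in use (A) and an add-on effect of 0.3 to 1.0 m/s (A): 0.2 × 0.3 = 0.06 m/s to 0.2 × 1.0 = 0.20 m/s.

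*Within an arm.* For a fall from 155/95 to 135/85 mmHg (A), mean pressure goes from (155 + 2×95)/3 = 115.0 to (135 + 2×85)/3 = 101.7, a fall of 13.3 mmHg. The PWV fall is 0.3 × 1.33 = 0.40 to 0.8 × 1.33 = 1.07 m/s, with no change in structure.

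*Heart rate.* Not quantified. The documents give no relation between heart rate and PWV. It is included because the comparator is a beta blocker and heart rate is already recorded.

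**The case against.** **Randomisation.** The off-treatment versus on-treatment contrast applies to both arms, which share a target and an add-on rule, so common pressure lowering cancels. This stands. A reader might infer that the V1/V4 difference in treatment state biases the section 6.2 comparison in itself; it does not. But equality at V4 is not assured. The protocol compares antihypertensive efficacy between arms as an objective, and add-on use depends on response to the randomised drug. The text on what follows a missed target also conflicts: sections 3.6.4 and 3.6.5 call for titration, whereas section 5.1 continues the regimen at V2 and V3 whenever BP is below 180/120 mmHg. Add-on timing conflicts too: the week 4 telephone visit in sections 3.6.3 and 5.1, week 8 in sections 3.1 and 3.8. These passages must be reconciled.

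**The protocol's own evidence.** Section 1.1 cites a meta-analysis in which stiffness fell whatever the size of the BP effect, and calls the structural effect long-term, which matters at 48 weeks. Its sentence on functional effects concerns antihypertensives other than moxonidine. All this is fair and supports a partly pressure-independent effect. It does not remove the pressure or add-on component, and it still covers the comparator and both add-ons.

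**Definition.** Section 1.1 does not say that stiffness must be pressure-independent to count as ageing, and PWV is not the only vascular marker. Both stand. The point is therefore about interpretation: the raw contrast is not invalid.

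**Adjustment.** BP and heart rate at V4 are post-randomisation. Conditioning on them can remove a real effect or introduce bias. This stands, so an adjusted model cannot decide whether an ageing conclusion is allowed.

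**Standing of the endpoint.** PWV is secondary in an exploratory, unpowered trial, section 10.1 defers detail to a later SAP, and target-BP attainment is already compared by arm. This lowers the priority. But a dichotomised BP result does not show mean pressure beside PWV, and the text supplied contains no rule that does.

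**Conclusion.** The concern holds as a limit on interpretation. The between-arm PWV contrast validly estimates the total effect of the two strategies, including BP lowering and add-on. It does not support a statement about vascular ageing if the arms differ at V4 in BP, heart rate or perindopril/losartan use. The within-arm and historical-control reading in section 10.3 is affected even when the arms are equal.

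The size rests on assumption: 0.15 to 0.40 m/s for a 5 mmHg arm difference at 0.3 to 0.8 m/s per 10 mmHg, and zero if the arms reach the same pressure, heart rate and add-on use. A reader might take the 8% to 57% range as the trial's false-positive rate. It is not: it is conditional on that 5 mmHg difference, and it uses 57 per arm although efficacy is analysed in per-protocol completers, where fewer patients would lower it. A rejection would also reflect a real effect on PWV; only the label would be wrong.

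The primary endpoint is untouched. The change is worth making before the SAP is finalised.

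**What to change.** In sections 6.2 and 10.3, and in the SAP:

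1. Keep the between-arm PWV comparison, name it as the total effect of the treatment strategies, and adjust it for V1 PWV.
2. Report beside it, by arm, mean arterial pressure and heart rate at V1 and V4, and perindopril/losartan use.
3. Add one pre-specified supportive model that also adjusts for same-visit mean arterial pressure and heart rate. Label it as conditioning on post-randomisation variables, and do not use it as a decision rule.
4. State that a PWV difference, or a within-arm fall, will be described as a treatment effect including BP lowering and add-on use, and not on its own as slowed vascular ageing.

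The cost is one extra regression on data already collected, a small table and some wording. The downsides are that the adjusted estimate is not a causal pressure-independent effect, and that the trial can claim less from PWV.

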### **Treatment regimens**

- **Group 1** patients receive moxonidine with dose titration up to the maximum, then a patient may be switched to the combination therapy, if necessary (step 2 - adding an ACE inhibitor).
- **Group 2** patients receive bisoprolol with dose titration up to the maximum, then a patient may be switched to the combination therapy, if necessary (step 2 - adding an ACE inhibitor).

The investigator will provide a Group 1 patient with moxonidine 0.4 mg in the amount required for 56 days of treatment plus 7 extra days and additionally moxonidine 0.2 mg in an amount required for 42 days of treatment if the dose is titrated up to 0.6 mg/day.

The patient will take the first moxonidine tablet immediately during the visit after all the visit procedures are completed. The patient will be instructed to take 1 tablet of moxonidine 0.4 mg in the morning, daily. The next visit will be scheduled in week 8 after the enrollment visit (in 56 days  $\pm$  5 days after the enrollment visit).

The patient will be asked to bring all the blisters of investigated product (empty, started and not started blisters) to every visit after the study initiation.

The investigator will give the patient blood pressure self-monitoring diary which is to be used by the patient to daily document her BP values and to bring it to every subsequent visit.

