#### **Secondary Endpoints:**

- To assess mean values of osteocalcin at visit 4 versus baseline level (visit 1) and to compare the values between the groups
- To assess mean values of the receptor activator of nuclear factor kappa-B ligand (RANKL) at visit 4 versus baseline level (visit 1) and to compare the values between the groups
- To assess mean values of BMD at visit 4 versus baseline level (visit 1) using control dual-energy X-ray absorptiometry and to compare the results between the groups
- To assess mean telomerase activity at visit 4 versus baseline level (visit 1) and to compare the values between the groups
- To assess mean pulse wave velocity (PWV) at visit 4 versus baseline level (visit 1) and to compare the values between the groups
- To assess mean intima-media thickness (IMT) at visit 4 versus baseline level (visit 1) and to compare the values between the groups
- To estimate the proportion (%) of patients who achieved target blood pressure <140/90 mmHg at the visit 2 (Week 8), 3 (Week 24) and 4(Week 48) and according to the patient's diary.

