### **7.2 Methods and timing**

Methods and timing of the parameters identification are as follows:

**Physical examination.** During the patient screening and enrollment and at the final visit, the investigator will document the patient's complaints and abnormalities, detected on

physical examination. All clinically significant abnormalities should be reported as adverse events.

**Blood pressure and heart rate.** All patients will have their blood pressure and heart rate measured at every visit. If blood pressure and heart rate are abnormal, the investigator will evaluate the clinical significance of the abnormality and decide on whether to document it as an adverse event.

**Laboratory tests parameters:** creatinine (including creatinine clearance calculation according to Cockcroft-Gault equation), potassium, sodium, ALT, AST. Fasting blood samples will be obtained at screening and at the final visit. Results of the tests will be entered into the CRF. If the sample is lost, the investigator may order resampling if medically indicated (e.g., if invalid test results are suspected).

All clinically significant adverse deviations from the baseline (screening) will be reported as adverse events.

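### Blood pressure efficacy is analysed only as the yes/no target below 140/90 mmHg; a baseline-adjusted mmHg difference from readings already taken would be more precise

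*Combined protocol and SAP*

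**What the plan says.** Section 2.2 sets the objective as a comparison of two drugs: "To investigate efficacy of antihypertensive therapy with moxonidine versus bisoprolol in hypertensive postmenopausal women".

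The endpoint lists in the synopsis and in sections 3.10, 6.2 and 10.3 turn this into one kind of blood pressure measure. Section 6.2 gives it as "Proportion of the treatment responders (defined as the proportion (%) of patients who achieved target blood pressure <140/90 mmHg", at V2, V3 and V4, compared between groups. Section 10.3 opens more broadly, "The treatment efficacy will be evaluated on visits V2, V3 and V4 based on SBP and DBP measurements", but then reduces the readings to two classes: "Responders: hypertension control, if BP <140/90 mmHg at the visit", and non-responders otherwise. No list contains mean SBP or DBP, or a change in either.

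Numeric readings exist. Section 7.2 states: "All patients will have their blood pressure and heart rate measured at every visit". Sections 3.6.2 and 3.6.4 to 3.6.6 call for the average of three seated readings at V1 and of two at V2, V3 and V4. Home pressure is also kept in a diary "which is to be used by the patient to daily document her BP values". Section 3.10 names the diary as a further source for the same proportion ("and according to the patient's diary"); sections 6.2 and 10.3 do not mention it.

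Section 10.1 sets two-sided tests at 0.05 and provides means, SDs and confidence intervals as general summaries of interval-scale variables. Section 10.3 says efficacy results will be presented descriptively. Section 10.5 describes an exploratory trial with no formal sample size calculation.

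**The concern.** Every other secondary endpoint in section 6.2 is a mean change from V1. Only blood pressure is dichotomised and separated from its baseline. Entry SBP runs from 140 to below 180 mmHg (section 4.2). If DBP is below 90 at the visit, a woman who falls from 178 to 142 (36 mmHg) is a non-responder, and one who falls from 142 to 138 (4 mmHg) is a responder.

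Two things are at stake. The comparison under objective 3 is less precise than the collected data allow. And PWV and IMT are secondary endpoints whose between-arm differences are easier to interpret beside a between-arm difference in mmHg, which the plan does not name.

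**Working it through.** **Plan's own figure.** There is no power figure to reproduce. The 114 in section 10.5 comes from feasibility: 300 screened at about 3 to 1 gives 100, the stated minimum, and 114 is the ceiling. No SD, expected difference or responder rate is given for blood pressure.

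**Inputs from the documents.** 57 per arm (section 3.2); two-sided alpha 0.05 (section 10.1); cut-off 140 mmHg.

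**Assumptions.** SBP only, normally distributed, SD 14 mmHg; comparator mean 138 mmHg at V4; the other arm lower by 7, 5 or 3 mmHg; V1–V4 correlation r = 0.4 or 0.2. The direction is arbitrary.

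**Responder test, 7 mmHg gap.**
- p1 = Φ((140 − 138)/14) = 0.557; p2 = Φ((140 − 131)/14) = 0.740; difference 0.183; mean p = 0.648.
- SE under the null = √(2 × 0.648 × 0.352/57) = 0.0894. SE under the alternative = √((0.557 × 0.443 + 0.740 × 0.260)/57) = 0.0878.
- Power = Φ((0.183 − 1.96 × 0.0894)/0.0878) = Φ(0.09) = 54%.

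**t-test.** SE = 14 × √(2/57) = 2.62 mmHg; 7/2.62 = 2.67; noncentral t on 112 df gives 75%.

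**ANCOVA.** Residual SD = 14 × √(1 − r²). At r = 0.4 this is 12.83, SE 2.40, 7/2.40 = 2.91, power 82%. At r = 0.2 it is 13.72, power 77%.

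The same formulas at each gap:

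| Gap at V4 | Responder rates | Responder test | t-test | ANCOVA, r = 0.4 |
|---|---|---|---|---|
| 7 mmHg | 56% v 74% | 54% | 75% | 82% |
| 5 mmHg | 56% v 69% | 32% | 47% | 54% |
| 3 mmHg | 56% v 64% | 14% | 21% | 24% |

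The gain from responder test to ANCOVA is 28, 22 and 10 percentage points. Most of it comes from keeping the scale rather than from the baseline adjustment: at r = 0.2 and 7 mmHg, ANCOVA gives 77% against 75% for the t-test.

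**Checks on the assumptions.**
- *Evaluable number.* Efficacy is analysed in completers (section 10.3). At 50 per arm and 7 mmHg the three figures are 48%, 70% and 77%.
- *Joint rule.* A simulation of SBP below 140 and DBP below 90 (57 per arm, difference 6/3 mmHg, SD 12/8, SBP–DBP correlation 0.5, baseline correlation 0.4) gave 51–53% for the responder test, 74–76% for the t-test on SBP and 82% for ANCOVA.
- *Responder rate.* The asymptotic efficiency of the cut variable relative to the continuous one is φ(c)²/(p(1 − p)), where Φ(c) = p: 0.64, 0.58, 0.49 and 0.34 at p = 50%, 70%, 80% and 90%. The loss is largest where most women reach target, which is what titration aims for.

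**Precision.** With the 7 mmHg inputs, the 95% CI half-width is about 1.96 × 0.0878 = 17 percentage points for the responder difference. It is 1.98 × 2.62 = 5.2 mmHg for the unadjusted SBP difference and 1.98 × 2.40 = 4.8 mmHg with r = 0.4.

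**The case against.** The strongest objection is the treat-to-target design. Under sections 3.1 and 5.1, doses in both arms are raised towards the same target and perindopril may be added in either. This tends to pull the arms together by V4, so a 7 mmHg gap may be optimistic; at 3 mmHg neither scale has useful power. That stands, and is why smaller gaps are shown. It limits the gain but does not reverse it: the responder test is weaker in every scenario tried. The same design means a mmHg difference compares two strategies that include the add-on; a reader might take it as the drugs' own effect, and the plan does not support that.

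The correlation of 0.4 is also unsupported. Restricted entry SBP and response-driven treatment could both lower it. This too stands; most of the gain survives without it.

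Third, the trial is exploratory and was not sized on any endpoint, so a reader who infers that objective 3 falls short of a planned power would be wrong: none was planned. But section 6.2 asks for a comparison and section 10.1 for two-sided tests and intervals, so precision still matters.

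Fourth, the responder proportion is coherent: its threshold is the treatment target. It should stay.

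A reader might also infer that PWV and IMT cannot be interpreted at all. That goes too far, because section 10.1 permits descriptive blood pressure means. What is missing is a named between-arm contrast.

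Last, the diary does not strengthen the dichotomisation argument. Its absence from sections 6.2 and 10.3 is a separate gap in specification. Nothing says daily values enter the paper CRF; at V2 to V4 the investigator only reviews the diary. A seven-day mean before each of three visits would mean 7 × 3 × 114 = 2,394 diary days to transcribe, so a diary endpoint may not be free.

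**Conclusion.** The point holds as an inexpensive improvement, not as the repair of an error. Objective 3 is served only by a yes/no measure, although averaged clinic SBP and DBP are recorded at baseline and at every later clinic visit. Under the stated assumptions (57 per arm, SBP only, SD 14, comparator mean 138 mmHg), moving from the responder test to ANCOVA with r = 0.4 gains between 10 points of power at a 3 mmHg gap and 28 at 7 mmHg. The direction is robust to the assumptions tried; the size is not known, because the documents supply no SD, expected difference or correlation. Shared titration and add-on therapy make the lower end plausible.

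**What to change.** In sections 3.10, 6.2 and 10.3, and in the synopsis, add as an exploratory secondary endpoint the between-arm difference in clinic SBP and in clinic DBP at V4, estimated by ANCOVA adjusted for the V1 value of the same variable and reported in mmHg with a 95% CI. Report V2 and V3 the same way as supportive results. Keep the responder proportion beside them. State that the contrast includes titration and add-on therapy, and present it with the PWV and IMT results.

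Summarise diary pressure as a mean only if daily values are already captured in the database. Either way, say how the diary part of the section 3.10 endpoint will be analysed, or remove it.

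The cost is wording in the protocol and SAP, and up to six more nominal comparisons (two pressures at three visits). The documents set no multiplicity control, hence the exploratory label. No new clinic measurement is needed and no treatment rule changes.
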